4.7 Recruitment methods

All groups will be identified by the project manager and emphasis will be placed on recruiting patients antenatally as much as possible. The project manager is a member of the participants care team. The project manager will organise the recruitment and written consent, which can be obtained by any one of the research team members that will have been trained (expected to be up to 8 doctors and midwives on the delivery units of both QCCH and SMH although primarily it will be at QCCH). These doctors and midwives will undergo induction and then maintenance training in the study protocol, transperineal ultrasound and data entry/governance

including GCP training. Where a midwife performs the ultrasound examination, it will not be the same midwife responsible for the ongoing care and digital VEs of that woman: another midwife or doctor should perform the examination. Where a doctor performs the ultrasound examination, that doctor will not make the decision for a course of action, it will normally be made by the next most senior doctor. Ultrasound examinations should not be the basis for a course of action unless a clinically unexpected and important situation that would change clinical management is not disclosed through digital VE but is through ultrasound.

Ahead of recruitment, a press release on the Imperial College Healthcare NHS Trust and Imperial College website will display recruitment posters. We will advertise on other relevant websites and display recruitment posters at other sites.

Recruitment areas

- Patient's attending the Early Pregnancy Unit (≤ 20 weeks gestation)
- Antenatal Clinic (all trimesters)
- Parent Craft classes (second and third trimester)
- Fetal Medicine Unit (all trimesters)
- Day Assessment Unit, Maternity Triage and Labour Ward (≥ 20 weeks gestation).

The project manager will organise a formal meeting with the charge nurses from all areas to inform them of the study upon ethics approval.

4.8 Consent and Information leaflet

(see supporting documents)

All participating patients will be consented prior to enrolment, and will receive a full explanatory information leaflet. All recruiters will be GCP trained.

4.9 Method of study

For each of the **two individual studies**, a **separate** information leaflet detailing the purpose will be provided to all potential recruits (see supporting documents and flow chart- **figure 7**). If a patient is willing to participate, written consent will be obtained.

The patients will then take part in a researcher led Reproductive Health interview which includes routine demographic data and information regarding previous obstetric, medical and gynaecological history, as well as questions regarding psycho-sexual health history. Where possible, the demographic and sensitive information relating to participants such as the ethnicity, obstetric and mental health history will be obtained by the researcher from the participants notes. All information will be entered into a secure study database. Patients will be identified by study number only.

During the ultrasound examination, women will be in the supine position with flexed hips and knees and the bladder empty as previously described. Healthcare professionals will be blinded to the ultrasound findings and these findings will also not be disclosed to the parents. Another doctor or midwife will perform all the ultrasound examinations.

Fetal position will be assessed with a transabdominal scan and recorded with half hourly divisions⁷. Thereafter, the transducer will be placed transperineally at the level of the posterior fourchette in a transverse position (Figure 1), and cervical dilatation¹⁴ and head-perineum distance (HPD) measured as previously described²². Caput succedaneum will be measured in a sagittal transperineal scan^{9,15} (Figure 1). Moulding will be assessed as either present or not¹².

The healthcare professional will perform digital vaginal examination assessing cervical dilatation, fetal head descent and position. The descent will be categorised using the WHO classification of fetal head station with the ischial spines as reference point 0, -5cm at the pelvic inlet and +5cm at the pelvic outlet²⁷.

Acceptability and Feasibility:

In this group, patients will also be asked to complete two additional researcher-led questionnaires (modified from a previously validated questionnaire -see supporting documents). This will be in the form of a “pre-study” and a “post-study” questionnaire which will focus on the patient’s views regarding vaginal examinations and the transperineal scanning method to assess the acceptability of the technique.

Transperineal ultrasound will then be carried out between gestations 24-42 weeks when a vaginal or speculum examination is otherwise also required to assess acceptability and feasibility. This scan will be done either immediately before or after the digital vaginal examination and the timing in relation the digital vaginal examination will be recorded.

Predictive Model:

In the predictive model group, there are no additional questionnaires. An admission ultrasound scan will be performed when the patient is deemed to be in established labour by the attending clinician. Subsequent scans will be performed as required at the time of routine clinical examinations typically between 2-4 hours apart.

The admission ultrasound scan will include if feasible fetal Doppler assessment of the umbilical artery, the cerebro-umbilical ratio (C/U: MCA/PI)¹⁶. Amniotic fluid index will also be measured. Fetal position will be assessed with a transabdominal scan and recorded as described above.

Dataset

Fixed variables

Maternal

Gestation

BMI, Age²⁸, Parity, Height, Ethnicity

Contraindication to vaginal examinations

Reason for avoidance of vaginal examinations

Fetal

EFW if known

Singleton

Multiple

Intrapartum

Non-USS:

Rupture of Membranes Yes/No: If Yes: Time

Spontaneous onset of labour Yes/No: If Yes: Time

Induction of Labour with prostaglandins Yes/No: If Yes: Time at insertion of prostaglandin

Syntocinon Yes/No: If Yes: Time
Epidural analgesia Yes/No: If Yes: Time

Modifiable parameters

USS Parameters: modified as labour progresses

- head position (TA ultrasound scan)
- cervical dilatation
- head-perineum distance
- caput
- moulding

Prolonged first stage of labour will be diagnosed according to national guidelines set in the UK by the National Institute of Health and Clinical Excellence (NICE) guidelines (cervical dilatation of < 2 cm in 4 hours)²⁵.

If recruited to the study, all patients will undergo normal clinical management with digital VEs or speculum examination performed as planned and in addition, ultrasound examinations before the digital VE/speculum by trained professionals. These ultrasound examinations will be blinded to the normal caregivers (midwives or doctors) so that they do not influence clinical management, though for practical reasons it will not be possible to blind the ultrasound operator to the clinical findings.

In women where **digital** vaginal examinations are contraindicated, we will compare ultrasound observations to those obtained by speculum. In all other women, ultrasound measurements will be compared to the corresponding digital vaginal examinations. In women who decline **digital** vaginal examinations for psychological reasons, this will be noted.

There are no additional visits outside the normal care pathway for the patient. The length of years of obstetric experience of the healthcare professional carrying out the digital vaginal examinations, speculums, ultrasound scan and the delivery will be recorded.

Study Timeline

The study will run according to the following timeline:

- **Months 0-3:** Ethics completion, staff training, and setting up web based study screens
- **Months 3-27:** Active study recruitment
- **Months 27-36:** Analyses and write up of an ultrasound based labour record (the sonopartogram) and development of a predictive model.

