4.14 External peer review

An earlier version of this protocol has been subject to external peer review by the British Medical Association leading to external funding (Helen Lawson Grant, awarded July 2014)

5. Study Outcome Measures

5.1 Primary measures:

1. Assessing feasibility of ultrasound by comparison with digital vaginal examinations:

- *Digital vaginal examination*: cervical dilatation, head station, caput, moulding, head position
- *Ultrasound*:
 - *Transabdominal Ultrasound*: Fetal head position
 - *Transperineal Ultrasound*: Cervical dilatation, head-perineum distance, caput and moulding

2. Acceptability of Transperineal Ultrasound to patients

3. Dataset for predictive model of outcome of labour of Caesarean section due to failure to progress and/or fetal distress

- Time to delivery

- Mode of delivery
- Primary indication for delivery
 - failure to progress
 - suspected fetal compromise

5.2 Secondary measures:

1. Neonatal outcome

- Gender
- Birth-weight
- Apgar Scores at 1 and 5 minutes
- Cord Gases
 - Fetal acidosis defined as arterial pH <7.10 and base excess >12.0mmol/l
- Neonatal unit admission within 24 hours
- Neonatal morbidity

6. Adverse events and reporting procedure

RISK ASSESSMENT - This study will not involve any risk to the participants. There are no predicted risks associated with the additional transabdominal and transperineal ultrasound scan. The scans will be used at the same settings and duration as routine ultrasound. We will be using probe covers and disinfection spray to clean the probe between patients.

The patient will be managed accordingly in concordance with local guidance and follow up arrangements will be made. The patient will still be followed up for the purposes of the study.

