7.1 Statistical and Data Analysis

In both groups, data will be collected prospectively and compared with vaginal examinations. In the second group, there will also be additional longitudinal measurements.

We will use a p value of <0.05 to indicate significance.

All measurements will be entered online at the time of examination to a secure database on the Imperial College Healthcare NHS Trust shared server where the patient will be identified by study number only. The database entry page will be accessible to investigators on their login, though they cannot interrogate data already entered. The data rules will follow closely to those performed through the recently completed multicentre European TRUFFLE study of fetal growth restriction where ultrasound measurements were captured at the time of examination³⁷.

For 24-42 weeks assessment of acceptability and feasibility:

Acceptability and preference will be tested using a questionnaire with Likert scale for discomfort, adapted from the W-DEQ Score³⁸

Feasibility of the ultrasound technique will be compared to digital VE for (a) total number of observations missing (head descent, position and cervical dilatation) during an admission on the delivery unit and (b) number of ultrasound examinations or digital VEs that could not be carried out for whatever reason where there was an intention to carry out a digital VE.

As a part of feasibility, *Reproducibility* between the *ultrasound and digital VE techniques* will be assessed both as a correlation (r) and agreement (using the Bland Altman method) between the ultrasound method and digital VE for head descent and cervical dilatation, and the Kappa statistic for head position.

Term predictive model:

The predictive value of intrapartum ultrasound parameters will be investigated using linear and logistic regression analyses. We will calculate the Receiver Operating Characteristic (ROC) curve with the Area Under the Curve (AUC) and associated positive and negative predictive values for delivery outcomes in the evaluation of transperineal ultrasound as a diagnostic tool.

8. Study supervision and Monitoring

Central and local supervision: the chief principal investigator at Imperial College London will be responsible for the protocol, quality control, interim analyses of the data, advice on progress and final analysis and reporting of the study. The Imperial Joint Research Compliance Office may audit the study as part of routine research governance.

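### The post-study acceptability questionnaire is researcher-led and may be administered by the person who did the scan, which may inflate the ratings of ultrasound

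*Combined protocol and SAP*

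**What the plan says.** Section 5.1 lists "Acceptability of Transperineal Ultrasound to patients" as the second primary measure. Section 4.9, under Acceptability and Feasibility, gives the mode of collection: "In this group, patients will also be asked to complete two additional researcher-led questionnaires". There is one form before the study and one after it, "which will focus on the patient’s views regarding vaginal examinations and the transperineal scanning method to assess the acceptability of the technique". Section 7.1 describes the instrument: "Acceptability and preference will be tested using a questionnaire with Likert scale for discomfort, adapted from the W-DEQ Score".

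Section 4.7 describes the staff. Written consent is something "which can be obtained by any one of the research team members that will have been trained", and the team is expected to number up to 8. It continues: "These doctors and midwives will undergo induction and then maintenance training in the study protocol, transperineal ultrasound and data entry/governance". A midwife who scans may not be the one responsible for that woman's care and VEs. The same section adds: "The project manager is a member of the participants care team".

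The text supplied does not say who leads the questionnaires. It has no self-completion, no rule keeping the scan operator away from the post-study form, and no record of how the form was completed.

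**The concern.** Discomfort and preference are subjective judgements about two intimate examinations. A woman who gives them to a researcher may soften what she says about a procedure which that researcher, or a close colleague, has just performed. The study hypothesis in section 2.2 is that the scan is acceptable compared with VE, so softening of the scan rating would push the result towards the hypothesis.

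The estimate itself is at stake. Section 7.1 sets no cut-off on the Likert scale and no threshold for success, so the reported proportion and the stated preference are the finding. Answers given face to face cannot be corrected at analysis, and a larger sample does not dilute a systematic shift.

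**Working it through.** **Who may lead the form.** The questionnaires are researcher-led (4.9), and the consenting team is trained in the scan and in data entry (4.7). The separation rules in 4.7 and 4.9 concern scan against VE and scan against clinical decisions. None concerns scan against questionnaire. Overlap between scan operator and interviewer is therefore permitted, though not stated.

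**Which form is exposed.** Section 4.9 introduces the questionnaires and then has the scan carried out. The pre-study form cannot carry courtesy about a scan not yet experienced, so the concern is confined to the post-study form.

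**The plan's own figure.** Inputs from section 7: 68% acceptability for ultrasound, 20% for VE, alpha 0.05, power 90%, minimum 42. Taking a two-sided test of two independent proportions (sidedness is not stated):

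n per group = [1.960 × √(2 × 0.44 × 0.56) + 1.282 × √(0.68 × 0.32 + 0.20 × 0.80)]² / 0.48² = (1.376 + 0.788)² / 0.2304 ≈ 20.3, so 21 per group and 42 in total.

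The figure reproduces. The independent-groups formula is kept below only to match it; whether it suits women who rate both methods is a separate question.

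**Illustration only.** The documents give no size for the bias, so the values below are assumptions. With d the difference, p̄ the mean proportion and q = 1 − p:

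power = Φ{[d√n − 1.960 × √(2p̄q̄)] / √(p₁q₁ + p₂q₂)}

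The sample of 100 ratings per method comes from the expectation of at least 100 questionnaires in section 7.

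(a) Suppose some of the 68% is courtesy and VE stays at 20%:

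| Inflation (points) | True contrast | Total n for 90% power | Power, 21 per method | Power, 100 per method |
|---|---|---|---|---|
| 0 | 68 v 20 | 42 | 91% | >99% |
| 5 | 63 v 20 | 52 | 83% | >99% |
| 10 | 58 v 20 | 66 | 73% | >99% |
| 20 | 48 v 20 | 118 | 48% | 99% |

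Courtesy alone would have to be worth 68 − 20 = 48 points to create the whole assumed gap.

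(b) Suppose the two methods are truly equal and only the ultrasound rating is inflated. The chance of a significant result favouring ultrasound, for a common true rate of 20%, 50% or 68%, is:

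| Inflation (points) | 21 per method | 100 per method |
|---|---|---|
| 10 | 11%, 9%, 11% | 37%, 29%, 36% |
| 20 | 29%, 26%, 34% | 88%, 83%, 93% |

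Check of one cell (30% v 20%, n = 100): (0.10 × 10 − 1.960 × √0.375) / √0.37 = (1.000 − 1.200) / 0.608 = −0.329, and Φ(−0.329) = 0.371.

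Under (a) the direction of the conclusion survives and the size is overstated. Under (b) more questionnaires make a false conclusion more likely.

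**The case against.** The strongest reply is that the documents do not establish the bias. They do not name the interviewer, and the questionnaire sits in supporting documents that were not supplied. Researcher-led could mean that a researcher hands over and explains a form which the woman marks herself. This stands: the point is a risk that the text permits.

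A reader might infer that the bias is strictly one-sided, because the scan belongs to the research team and the VE to someone outside it. The documents do not say that. The separation is made woman by woman, the trained staff work on the delivery units, and the project manager is in the care team. Some courtesy may therefore attach to the VE as well and partly cancel in the comparison. Nor should the recruitment publicity in 4.7 be read as the team promoting the scan; it advertises the study.

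Two possible safeguards do not answer the point. Study numbers protect stored records, but the woman still answers to a researcher. Modifying a validated questionnaire does not settle how it should be administered.

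Finally, researcher-led collection can be defended as keeping forms complete in women who may be in labour. That is a real trade-off, and the fix carries it as a cost.

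**Conclusion.** The concern holds as an avoidable risk of social-desirability bias in a primary patient-reported measure, confined to the post-study form and more likely than not to favour ultrasound. Its size is unknown. If the true contrast is anywhere near 68% against 20%, a moderate bias would inflate the estimate and would be unlikely to reverse the conclusion. It matters more if the true gap is small, and it bears directly on the reported acceptability and preference because no threshold is set.

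This rests on two assumptions: that the supporting documents hold no safeguard missing from the protocol, and that courtesy towards the scan is not fully matched by courtesy towards the VE. A reader might go further and put a definite number of points on the error, or conclude that the acceptability result could not be believed. The documents support neither, since they give no rate at which women soften their answers.

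**What to change.** In section 4.9, change the discomfort and preference items of the post-study questionnaire from researcher-led to self-completed. Have each woman rate ultrasound and VE on the same Likert scale, on a form that carries only her study number and is returned sealed. Where she needs help, it should come from an existing team member who did not perform her scan. Record the mode of completion, so that assisted forms can be reported separately. Help from the same team leaves some residual risk, which that record makes visible.

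The reproductive health interview and the pre-study form can stay researcher-led. The cost is protocol wording and form layout, with no extra staff or visits. The downside is somewhat more incomplete forms among women in labour. The change should be made before data collection starts.

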A recent study by our group has shown that 95%¹⁵ of transperineal ultrasound parameters can be obtained compared to 82% of digital vaginal examination parameters¹⁵. With an alpha of 0.05 and a power of 90%, the minimum sample size required is 250 patients.

Labour prediction model

For the labour prediction model, there are approximately 15 variables with 10 patients needed per variable³²⁻³⁴ and an approximate 25% Caesarean section rate^{28,35,36} (the primary outcome) in the UK currently. This equates to 600 patients needed for the study.

Calculation:

$$15 \times 10 \times (100/25) = 600 \text{ patients}$$

As already discussed above, for statistical power and significance, a minimum of 42 and 250 patients is required for acceptability and feasibility respectively (24-42 weeks). For the predictive modelling, 600 patients are required (37-42 weeks).

The majority of the patients for the acceptability and feasibility samples will be recruited from the predictive modelling group (gestation 37-42 weeks). However, to allow sufficient data collection for feasibility, acceptability and development of the model, at least 700 patients will be required. As the trust has an annual delivery rate of 9000 annually, over a 24-month data collection period with a delivery rate of 18,000 across the trust, 700 patients (4%) sample size is achievable.

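### Feasibility count (a) in section 7.1 is limited to delivery-unit admissions, although section 4.9 schedules the feasibility scan at any vaginal or speculum examination needed at 24-42 weeks

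*Combined protocol and SAP*

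**What the plan says.** The hypothesis in section 2.2 is that transperineal ultrasound is feasible and acceptable across 24 to 42 weeks. Section 4.9 (Acceptability and Feasibility) fixes when the scan takes place: "Transperineal ultrasound will then be carried out between gestations 24-42 weeks when a vaginal or speculum examination is otherwise also required". It names no clinical area. Section 4.9 adds that for women in whom digital "vaginal examinations are contraindicated, we will compare ultrasound observations to those obtained by speculum".

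Section 7.1, in the part on the 24-42 week assessment, gives three feasibility analyses and ranks none of them above the others:

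- Count (a) is the "total number of observations missing (head descent, position and cervical dilatation) during an admission on the delivery unit".
- Count (b) tallies failed attempts with either method, namely those "that could not be carried out for whatever reason where there was an intention to carry out a digital VE".
- Correlation and Bland-Altman agreement are assessed "between the ultrasound method and digital VE for head descent and cervical dilatation, and the Kappa statistic for head position".

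Only (a) names a place. Section 7 sizes feasibility at 250 patients, from 95% of parameters obtained by ultrasound against 82% by digital VE. It expects most of these patients to come from the term labouring group used for the prediction model.

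**The concern.** Count (a) is the analysis closest to the quantity behind the sample size, because observations missing are the complement of parameters obtained. If (a) is confined to delivery-unit admissions, it leans towards women in labour. The sample already leans that way, since most feasibility patients are drawn from the term labouring group. The examinations left out would come from the minority who represent the rest of the 24-42 week range. Whether a scan yields descent, position and dilatation may differ between those settings, so a result from (a) could be reported as holding for 24-42 weeks when it was observed mainly in labour. Counts (a) and (b) would also describe different sets of examinations and could not be read side by side.

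**Working it through.** **Coverage, by type of examination.** Applying the wording of section 7.1 to each type of occasion that section 4.9 admits:

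| Occasion at 24-42 weeks | Count (a) | Count (b) | Agreement |
|---|---|---|---|
| Digital VE intended, during a delivery-unit admission | yes | yes | yes, if both methods give a value |
| Digital VE intended, outside a delivery-unit admission | no | yes | yes, if both methods give a value |
| Speculum only, during a delivery-unit admission | unclear: no speculum comparator is named | no | no |
| Speculum only, outside a delivery-unit admission | no | no | no |

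The second row is the mismatch. The last row is a full gap: (b) requires an intended digital VE and agreement is measured against digital VE, although section 4.9 promises a speculum comparison.

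**Does it change the sample size or power?**

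1. Inputs from section 7: p1 = 0.95, p2 = 0.82, alpha 0.05, power 90%. Sidedness is not stated; two-sided is assumed.
2. The plan's figure, by the pooled two-group formula: n per group = [1.96 × √(2 × 0.885 × 0.115) + 1.2816 × √(0.95 × 0.05 + 0.82 × 0.18)]² / 0.13² = (0.884 + 0.566)² / 0.0169 ≈ 124.5. This rounds up to 125 per group, 250 in total, which is the stated figure.
3. The place restriction does not enter this formula, so removing it leaves 250 unchanged.
4. The share of examinations outside the delivery unit is not given. Purely as an assumption, losing a share of the 250 from (a) gives, on the same two-group formula:

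| Share lost | Power |
|---|---|
| 0% | 90.1% |
| 10% | 86.9% |
| 14% (about 100/700, from 700 - 600) | 85.3% |
| 20% | 82.7% |
| 30% | 77.4% |
| 50% | 62.7% |

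5. Section 4.9 has both examinations done in the same woman, so a paired calculation fits the design better. Assuming the two results are independent within a woman, the discordant probabilities are 0.95 × 0.18 = 0.171 and 0.05 × 0.82 = 0.041. Their sum is 0.212 and their difference 0.13. McNemar: n = [1.96 × √0.212 + 1.2816 × √(0.212 - 0.0169)]² / 0.0169 ≈ 127.6, so 128 women. On that basis, half of the 250 (125 women) still gives about 90% power.

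The power figures therefore depend on an unknown share and on the choice of formula. The coverage gap depends on neither.

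**The case against.** Four points can be made in the plan's defence.

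- A reader might infer that examinations outside the labour ward vanish from the feasibility result. The documents do not support that. Count (b) and the agreement analyses have no place limit, and (a) is not named as the single primary analysis. This objection stands, except for speculum-only examinations outside the delivery unit.
- A reader might take the recruitment list in section 4.7, with its entry "Day Assessment Unit, Maternity Triage and Labour Ward", as proof that study scans take place in triage or day assessment. It is a list of where women are approached. It also includes the Early Pregnancy Unit (up to 20 weeks) and antenatal classes, so it does not locate examinations. Section 4.7 also places the trained team on the delivery units. This stands.
- The term delivery unit is never defined. Section 2.1 uses it loosely enough to take in examinations done to rule labour out, so triage might be meant to fall inside it. This is possible, but it is a reason to define the term, and section 4.9 still sets no place limit.
- A reader might infer that feasibility becomes underpowered. That rests on an assumed share lost and on a two-group formula applied to paired examinations. In addition, 250 is a minimum within at least 700 women. The inference is not supported.

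None of this removes the literal difference between the scanning rule in section 4.9 and the counting rule in (a).

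**Conclusion.** The point holds for count (a). As written, (a) leaves out 24-42 week examinations made outside a delivery-unit admission, although section 4.9 brings them into the feasibility study. They remain in (b) where a digital VE was intended, and in the agreement analyses where both methods give a value. The consequence is that (a) cannot by itself support a conclusion for the whole 24-42 week range. The number affected cannot be derived from the documents. It is probably a minority, given that most feasibility patients come from the labouring group. The 250 stands, and no loss of power is established. The conclusion assumes that delivery unit does not cover every area where study examinations occur. If it does, a definition settles the matter for digital VEs, but speculum-only examinations would still be missing from (b) and from agreement.

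**What to change.** In section 7.1 (a), replace the delivery-unit restriction with: *at every study occasion between 24 and 42 weeks on which a digital VE or speculum examination was intended, in any clinical area*. Then:

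- Apply the same set of occasions to (b), so that the two counts can be read together.
- Report speculum-only occasions separately, in line with section 4.9, so that a contraindicated digital VE is not counted as a failed one. State which of the three observations a speculum is expected to supply. Wording that required an intended digital VE would leave these women out.
- Record the location of each examination (the section 4.9 dataset has no such field), define delivery unit, and show delivery-unit and other-area occasions as separate rows.

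If the restriction is intended, keep it, say so, and limit the conclusion from (a) to delivery-unit admissions.

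The cost is small: a few lines in section 7.1 and one extra data field, since measurements are already entered at each examination. The pooled set of examinations becomes more mixed, which the separate rows make visible. The sample size does not change.

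### Section 4.9 gives two incompatible scan orders with an unblinded ultrasound operator, and section 7.1 ignores the recorded order, so agreement for dilatation and head position may look too close

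*Combined protocol and SAP*

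**What the plan says.** Section 4.9 (Method of study) sets the order of scan and examination twice.

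- Under Acceptability and Feasibility: "This scan will be done either immediately before or after the digital vaginal examination". Which order was used is to be noted each time.
- In the closing paragraph after the dataset list, for all recruited patients: "ultrasound examinations before the digital VE/speculum by trained professionals".

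That closing paragraph blinds the usual caregivers to the ultrasound but adds that "it will not be possible to blind the ultrasound operator to the clinical findings". Elsewhere 4.9 has a different doctor or midwife perform the scans. For the predictive group, examinations are serial: "Subsequent scans will be performed as required at the time of routine clinical examinations typically between 2-4 hours apart".

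Section 7.1 places agreement within feasibility, which is the first primary measure in section 5.1. It plans correlation and "agreement (using the Bland Altman method) between the ultrasound method and digital VE for head descent and cervical dilatation", with kappa for head position. It gives two rules on data handling: "All measurements will be entered online at the time of examination to a secure database", and investigators have their own login "though they cannot interrogate data already entered". It does not mention the order of the two examinations.

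**The concern.** The statement for all patients includes the feasibility group, so the two orders contradict each other. Section 7 says most feasibility women will come from the predictive group, so one woman can fall under both.

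The order matters because blinding runs one way. The VE examiner does not see the scan, but the scan operator may know the VE. Bland-Altman limits and kappa describe how far two methods agree when each is read on its own. If some scan readings are drawn towards a known VE result, they show closer agreement than independent readings would. The plan collects the variable that separates the two kinds of pair and then does not use it, so a reader of the results could not tell which kind produced the agreement.

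**Working it through.** **1. The plan's own figure.** The feasibility sample rests on 95% against 82% of parameters obtained, alpha 0.05 and power 90% (section 7). With a two-sided test and no continuity correction, n per group = [1.96 × √(2 × 0.885 × 0.115) + 1.2816 × √(0.95 × 0.05 + 0.82 × 0.18)]² / 0.13² = 124.5. That rounds up to 125 per group, or 250 in total, which matches the plan. The calculation concerns completion, not agreement, so scan order does not affect it. The plan states no expected limits, kappa or precision for agreement.

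**2. Share of scan-after pairs, f.** The documents do not fix f.

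- If the closing paragraph governs everyone, f = 0.
- If the permission to scan afterwards covers only women outside the predictive group, the planned minima leave 700 − 600 = 100 such women. With one pair each and all scanned after, f = 100/700 = 0.143 over all women, or 100/250 = 0.40 over the feasibility minimum.
- If the permission also reaches predictive-group women, the documents set no ceiling.

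**3. Dilatation.** Assume a scan-after reading moves a fraction w of the way to the VE value. Let b be the mean difference between methods, in SDs of the differences. Then

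narrowing of the limits = 1 − √[1 − f + f(1 − w)² + f(1 − f)w²b²].

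| f | w | b = 0 | b = 1 |
|---|---|---|---|
| any | 0 | 0 | 0 |
| 0.143 | 0.2 | 0.026 | 0.024 |
| 0.143 | 0.5 | 0.055 | 0.039 |
| 0.40 | 0.2 | 0.075 | 0.070 |
| 0.40 | 0.5 | 0.163 | 0.128 |

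Example: f = 0.40, w = 0.5, b = 0 gives 1 − √(0.60 + 0.40 × 0.25) = 1 − √0.70 = 0.163. A simulation of 2 million draws agreed to within 0.001 in every non-zero cell.

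In centimetres, with an assumed error SD of 1 cm per method, the true limits are ±1.96 × √2 = ±2.77 cm. If half the scans followed the VE, they would be ±2.45 cm at w = 0.25 and ±2.19 cm at w = 0.5.

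The formula has one limit. If b² exceeds (2 − w)/[w(1 − f)], mixing the two kinds of pair widens the limits, although the mean difference still shrinks, to b(1 − fw). The lowest such threshold among the four non-zero cases is b = √3.5 = 1.87, at f = 0.143 and w = 0.5.

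**4. Head position.** Assume equal marginals, and that a share c of scan-after readings switches to the VE category. Chance agreement is then unchanged and kappa becomes k + f × c × (1 − k). With an assumed true k of 0.30:

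| f | c = 0 | c = 0.2 | c = 0.5 |
|---|---|---|---|
| 0.143 | 0.300 | 0.320 | 0.350 |
| 0.40 | 0.300 | 0.356 | 0.440 |

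Head position comes from the transabdominal scan, while the before-or-after sentence concerns the transperineal scan. Section 4.9 puts the transabdominal scan just ahead of the transperineal one in the same session, so applying the order to head position is an inference, though a reasonable one.

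**5. Precision if scan-after pairs leave the main analysis.** The 95% CI half-width of a limit of agreement is 1.96 × √[1/n + 1.96²/(2(n − 1))] SD, assuming one pair per woman.

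| n | Half-width (SD) |
|---|---|
| 250 | 0.212 |
| 238 (5% lost) | 0.217 |
| 225 (10% lost) | 0.224 |
| 150 (100 lost) | 0.274 |
| 25 | 0.679 |

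**The case against.** The strongest reply is that the concession about blinding sits in the paragraph that puts the scan first. In that order the paired VE result does not yet exist, so the clinical findings in question are most naturally the labour history and earlier examinations. The plan therefore does not admit unblinding to the paired result. Separate operators and the bar on querying entered data give further protection.

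Part of this stands. Knowledge of the paired VE is inferred from reading the two paragraphs together. The data-entry rules lower the risk, but they do not stop an operator hearing the result or seeing it in the notes. A separate operator and blinded caregivers protect the VE reading, not the scan reading. It also stands that scan-first leaves earlier VEs in the same labour known to the operator.

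The values of f are open to challenge as well. The 700 is a minimum, most feasibility women come from the predictive group, and women compared with speculum supply no digital pair. Serial scans dilute f: with an assumed three pairs per predictive woman, f = 100/(100 + 3 × 600) = 0.05, and the limits narrow by only about 2% at w = 0.5. So 0.14 and 0.40 are conditional scenarios, not bounds. None of this removes the contradiction or supplies the missing use of the recorded order.

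Finally, agreement is only one component of feasibility and has no stated threshold, and by-order reporting would still be possible after the fact because order is recorded. That limits the consequence, but a rule fixed in advance is more convincing than one chosen once the data are seen.

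**Conclusion.** The point holds and should be fixed. The two order statements in 4.9 conflict, the operator is not blinded, and 7.1 does not use the recorded order. Followed as written, the plan lets non-independent readings into the agreement analysis for dilatation and head position.

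The likely direction is towards agreement that looks too close. The size cannot be derived from the documents and may be nil. In the illustrations with f at 0.14 to 0.40 and a pull of 0.2 to 0.5, the limits are 2% to 16% too narrow and a kappa of 0.30 reads as 0.32 to 0.44. These figures rest on assumed values of w, c, b and kappa and on the stated conditions for f. Confidence is medium.

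The sample sizes and the missing-observation and not-carried-out comparisons are untouched. Nothing is claimed about the prediction model.

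**What to change.** **Section 4.9.** Reconcile the two statements on the scan-first order already written for all patients. Require the scan reading to be entered before the operator learns the paired VE result, without delaying care, in keeping with section 9.2.

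**Section 7.1.**

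- Base the main agreement analysis on scan-first pairs.
- Report agreement by recorded order, or with any scan-after pairs included, as a sensitivity analysis.
- Keep all pairs in the completion counts.
- State two limitations: order is not randomised, so a before/after difference may reflect case mix; and in serial examinations the operator may know earlier VEs.

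**Cost.** Wording in two sections and a small extra analysis on a variable already collected, with no change to sample size. Once scan-first is the rule, few pairs should be lost. At 5% to 10% of 250, the half-width of a limit rises from 0.212 to 0.217 or 0.224 SD. If scan-first proved hard to follow and 100 pairs were lost, it would be 0.274 SD. With only 25 scan-after pairs their own limit has a half-width of 0.68 SD, so the comparison by order should be descriptive.
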